10.1.1 Schema

Figure 5 Module 1 Schema: AZD4573 Monotherapy in Participants with r/r PTCL and r/r HL

AZD4573 Monotherapy Treatment

^a Dosing regimen based on AZD4573 monotherapy RP2D in lymphoma = 12 mg weekly.

^b Dose confirmation in first 6 participants/cohorts (safety/PK/PD) → SRC. Additional dose levels may be explored depending on the emerging clinical data in PTCL/cHL.

^c Twenty-one participants per cohort, and **CCI**

CCI

^d Twenty-one participants per cohort, and **CCI**

CCI

^e Primary analysis at N = 21 for each cohort, with the primary analysis after approximately 6 months or when 75% of participants have progressed or died (Section 10.6). Additional data cuts may also be performed if required.

Abbreviations: AE, adverse event; ALCL, anaplastic large cell lymphoma; BV, brentuximab vedotin; cHL, classical Hodgkin Lymphoma; CR, complete response, CTCAE, Common Terminology Criteria for Adverse Events; CTCL, cutaneous T-cell lymphoma; DCO, data cut-off; ECG, electrocardiogram; ECOG, Eastern Cooperative Oncology Group; N, number; NK PTCL, natural killer/peripheral T-cell lymphoma; ORR, overall response rate; PD, pharmacodynamic; PR, partial response; PTCL, peripheral T-cell lymphoma; r/r, relapsed/refractory; RP2D, recommended phase II dose.

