In addition to the initial safety run-in evaluation conducted separately within each cohort, pooled safety monitoring will be conducted every three months after the initial 15 dosed patients, pooled across the three cohorts, have had an opportunity to be treated for at least 8 weeks. If > 25% of participants experience any AEs related to study intervention that result in discontinuation of study treatment, the study data will be evaluated by the SRC. Enrolment may be paused until the safety data review by the SRC has been completed.

Other criteria for stopping or pausing the recruitment are described in Section 7.1.1.

CCI

If 1 or more cohorts show a favourable safety and efficacy profile by the primary analysis then further expansion cohorts may be added via a protocol amendment. The DCO for the primary analysis for each cohort will occur after all response-evaluable participants in the cohort have had the opportunity to be followed for at least 6 months since their first dose or have progressed or have initiated other anticancer therapy, or when 75% of participants have progressed or died, whichever occurs first. Additional data cuts may also be performed if required.

Table 10 Module 1: Planned Response-Evaluable Participant Population

Cohort	Population	Number of participants ^a	Line of therapy
Cohort 1	PTCL, all comers (excluding NKTCL)	21	2+
Cohort 2	PTCL (NKTCL only)	21	2+
Cohort 3	cHL	21	3+

^a CCI

Abbreviations: cHL, classical Hodgkin Lymphoma; NKTCL, natural killer/T-cell lymphoma; CCI [REDACTED]; PTCL, peripheral T-cell lymphoma.

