10.8.1.2 Disease Assessment Schedule

Baseline tumour assessments will be performed using radiologic imaging by CT with contrast and PET-CT during the screening period. CT scans with contrast will cover neck, chest, abdomen, pelvis and any other disease sites; PET scans will cover the whole body from base of skull to mid-thigh.

Radiologic scans (ie, contrast CT) and PET scans will be performed as specified in [Table 15](#)

below, and thereafter to confirm CR or as clinically indicated. Unscheduled radiologic scans may be performed at investigator discretion if deemed clinically indicated.

Table 15 Radiologic Scans and PET Scans for Tumour Assessments

Timepoints		Required radiologic scans ^a	
Screening		Contrast CT	PET
During study ^b	After 8 weeks (~2 cycles)	Contrast CT	PET
	After 17 weeks (~5 cycles)	Contrast CT	
	After 26 weeks (~8 cycles)	Contrast CT	PET
	After 38 weeks (~12 cycles)	Contrast CT	
	After 50 weeks (~16 cycles)	Contrast CT	PET
	After 62 weeks (~20 cycles)	Contrast CT	
	After 74 weeks (~24 cycles)	Contrast CT	PET
	After 86 weeks (~28 cycles)	Contrast CT	
	After 98 weeks (~32 cycles)	Contrast CT	PET
	Every 12 weeks (~4 cycles) thereafter until the end of the study	Contrast CT	
Every 24 weeks (~8 cycles) thereafter until the end of the study		Contrast CT	PET
30-day follow-up visit ^c		Contrast CT	PET

^a Following complete metabolic response, subsequent scheduled PET assessments are no longer mandatory.

^b Window of \pm 1 week for all timepoints.

^c Tumour assessments will be repeated at this visit for discontinued participants if not previously performed within the required timeframe ie 9 weeks for participants that discontinued before Week 26, and 12 weeks for those that discontinued after Week 26.

If a PET-CT is not available, an independent PET and a diagnostic-quality CT scan (with contrast) can be used. If PET and CT scans are done on the same day, the PET must be performed prior to the contrast-enhanced CT not to compromise the PET read-out.

Post screening, the CT portion of a PET-CT (without contrast) may replace a contrast CT per local institutional practice; however, certain radiographic requirements are needed for acceptance, as described in the Site Radiology Manual, provided separately from this protocol.

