4.2.1 Timing of Analyses

The DCO for the primary analysis for each Module 1 PTCL cohort (Cohorts 1 and 2) will occur after 21 response-evaluable participants in the cohort have had the opportunity to be followed for at least 6 months since their first dose or have progressed or have initiated other anticancer therapy, or when 75% of participants have progressed or died, whichever occurs first. If one cohort reaches its planned primary analysis DCO ahead of the other, then the slower enrolling cohort may be evaluated for efficacy responses at the same time. The purpose of evaluating the slower cohort early would be for internal planning and to review continued development of the AZD4573 in one or both r/r PTCL groups. When both cohorts have reached their primary analysis DCOs the efficacy and safety data may be pooled for analysis. Additional data cuts may also be performed, if required.

The DCO for primary analysis of the Module 1 cHL Cohort (Cohort 3) will occur after 21 response-evaluable participants in the cohort have had the opportunity to be followed for at least 6 months since their first dose or have progressed or have initiated other anticancer therapy, or when 75% of participants have progressed or died, whichever occur first. Additional data cuts may also be performed, if required.

At the end of the module a final analysis will be conducted to incorporate all data (up to and beyond the primary analysis) from all participants.

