4.2.2 Analysis Populations

For purposes of analysis, the study populations are defined as provided in [Table 2](#).

All participants who received any amount of IP will be included in the safety population.

The following populations are defined:

Table 2 Populations for Analyses

Population/Analysis set	Description	Endpoint/Output
Enrolled	All participants who sign the ICF.	Disposition
Safety	All participants who receive any amount of any IP.	Exposure Safety PK concentrations and parameters listings
Full analysis set/ITT	All participants who receive any amount of any IP.	Baseline and demography PFS OS
Response evaluable	All dosed participants who have measurable disease at baseline.	ORR CR DoR
Interim response evaluable	All dosed participants with measurable disease at baseline that have had their first post-baseline disease assessment performed or have discontinued study treatment before the first post-baseline disease assessment. This analysis set will not be used for presentation in the CSR and is only defined for conferences and publications.	ORR at interim DoR at interim
PK	All participants who receive any amount of IP with at least one reportable concentration.*	PK concentrations PK parameters

Abbreviations: ICF, informed consent form; IP, investigational product; ITT, intention-to-treat; PK, pharmacokinetics; PFS, progression free survival; OS, overall survival; DoR, duration of response; ORR, objective response rate; CR, complete response.

* Individual PK concentration and parameter data values that are excluded from the descriptive summary tables and/or figures eg, due to important protocol deviations that might effect PK – are included in the listings and are flagged with an appropriate footnote.

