5.2.1.2 Primary Analysis of Primary Endpoint: ORR

Summaries will be produced that present the number and percentage of participants with a tumour response (CR/PR) based upon the number of participants in the response evaluable analysis set. ORR will be calculated and binomial exact 2-sided CIs at 80% and 95% will be presented for participants in the response evaluable set. For the purpose of conferences and publications, outputs may also be presented for the interim response evaluable set.

A swimmer plot will be presented showing disease assessment results for each assessment performed, including treatment duration and treatment status.

In addition, BOR will be summarised by number of participants and percentage for each category (CR, PR, SD, PD, and NE). No formal statistical analyses are planned for BOR.

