Situation	Date of PD/Death or Censoring	PFS Outcome
Documented Progressive Disease (PD) or death in the absence of progression	Date of earliest documentation of PD or date of death in the absence of progression	Event
Either no assessment at baseline or no evaluable assessments post-baseline AND death prior to second scheduled post-baseline disease assessment	Date of death	Event
Either no assessment at baseline or no evaluable assessments post-baseline AND no death prior to second scheduled post-baseline disease assessment	Date of first dose (Day 1)	Censored
PD or death (in the absence of progression) immediately after ≥ 2 consecutive missed disease assessments as per the protocol specified assessment schedule	Last evaluable progression-free disease assessment prior to missed assessments	Censored
On-going with neither PD nor death at the time of analysis or lost to follow-up or withdrawn consent	Date of last evaluable disease assessment	Censored
Initiation of subsequent anti-cancer therapy prior to PD or death	Date of last evaluable disease assessment prior to initiation of subsequent anti-cancer therapy	Censored for sensitivity analysis only

Abbreviations: PD, progressive disease; PFS, progression-free survival

The PFS time is always derived based on scan/assessment dates, not timepoint dates.

Disease assessments/scans contributing towards a particular timepoint may be performed on different dates. The following rules are applied:

- The date of progression is determined based on the earliest of the dates of the component that triggered the progression.
- When censoring a participant for PFS the participant is censored at the latest of the dates contributing to a particular overall timepoint assessment.

Note: for target lesions only the latest scan date is recorded out of all scans performed at that assessment for the target lesions and similarly for non-target lesions only the latest scan date is recorded out of all scans performed at that assessment for the non-target lesions.

Duration of follow-up for PFS is applicable only for PFS censored participants and is defined as follows:

Duration of follow-up for PFS in censored participants (months) = (date of PFS censoring – date of first dose + 1) / (365.25/12).

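### The 75% event trigger for the primary data cut has no scan-opportunity condition, so a recently dosed participant can count as an ORR non-responder before the Week 8 scan

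*SAP*

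**What the plan says.** **Timing of the cut.** SAP 4.2.1 and protocol 10.9.2 join two branches. The first waits until 21 response-evaluable participants in the cohort have had a chance of six months' follow-up, or have progressed or moved to other anticancer therapy. The second is "or when 75% of participants have progressed or died, whichever occurs first". Protocol 1.1 and 10.4.1 carry the same second branch. Footnote e of the schema in protocol 10.1.1 adds "Primary analysis at N = 21 for each cohort".

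**Denominator.** SAP 4.2.2 defines the response evaluable set as "All dosed participants who have measurable disease at baseline". SAP 5.2.1.2 computes the response percentage "based upon the number of participants in the response evaluable analysis set". Under SAP 4.1.3.5 the only deviation that removes anyone is a missing baseline Lugano assessment.

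**Scans.** Table 15 of protocol 10.8.1.2 puts the first post-baseline scan at 8 weeks. SAP Appendix A gives its window as days 49 to 63. Participants who stop treatment without progression stay on the scan schedule (protocol 10.8.1.2). SAP 5.2.1.1 counts their responses, uses unscheduled as well as scheduled scans, and does not count a response first seen after subsequent anticancer therapy.

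**A related set.** SAP 4.2.2 also defines an interim response evaluable set, limited to those who have had a first post-baseline assessment or who stopped treatment before it. It is reserved for conferences and publications and is not used in the CSR.

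**Later looks.** SAP 4.2.1 allows further cuts ("Additional data cuts may also be performed, if required") and plans a final analysis at the end of the module.

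**The concern.** The two branches treat the most recently dosed participants differently. The first ensures that each of the 21 has either had six months in which to be scanned or already has an outcome. The second asks only for a count of events and says nothing about the participants without one. Someone dosed a few weeks before an event-driven cut is in the ORR denominator and, unless scanned early, cannot be in the numerator. That person's non-response reflects the calendar, not the drug.

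ORR is the primary endpoint, and protocol 10.4.1 links possible expansion cohorts to the profile seen by the primary analysis. The primary figure should therefore not depend on how many participants happened to be dosed just before the 16th event.

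**Working it through.** **Check on the plan's own figures.** The Week 8 window is 8 × 7 ± 7 = 49 to 63 days, which agrees with SAP Appendix A. The sample size of 21 cannot be reproduced because its precision tables are redacted; it is not in dispute here.

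**When the branch fires.** 0.75 × 21 = 15.75, so at the 16th event. That leaves up to 21 − 16 = 5 participants event-free, with any length of follow-up.

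**Cost per unscanned participant.** If k of 21 are unscanned and the true rate is p, expected observed ORR = p × (21 − k)/21.
- One unscanned: 30%/21 = 1.4 points at p = 30%, and 40%/21 = 1.9 points at p = 40%.
- All five unscanned at p = 30%: 30% × 16/21 = 22.9%.
- For scale, the standard error at p = 30% is √(0.3 × 0.7/21) = 10.0 points.

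**How often it would happen.** This depends on accrual and PFS, which the documents do not give, so both were assumed and varied. The simulation had 192 scenarios of 4000 trials each, with N = 21:
- true ORR 30% or 40%;
- first response at Week 8 in 100% or 75% of responders, the rest at Week 17;
- uniform accrual over 9, 12, 18 or 24 months;
- exponential PFS with median 1.5, 2.5 or 4 months for non-responders, and 5 or 10 months after response for responders;
- events dated either at the next scheduled scan or when they occur. SAP 5.2.4.2 ("The PFS time is always derived based on scan/assessment dates, not timepoint dates") is closer to the first; deaths and unscheduled scans put the truth between the two.

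Reading (a) cuts at the 16th event whether or not 21 are dosed. Reading (b) also waits for the 21st first dose, as footnote e suggests. Unscanned means dosed, under 8 weeks and event-free at the cut. Loss is unscanned eventual responders divided by the number dosed.

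| | Scan-dated (a) | Scan-dated (b) | Event-dated (a) | Event-dated (b) |
|---|---|---|---|---|
| Median loss over scenarios, points | 0.3 | 0.3 | 0.7 | 0.8 |
| Maximum loss, points | 1.8 | 2.5 | 2.5 | 3.6 |
| Trials with at least one unscanned, median | 11% | 12% | 25% | 27% |

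The event branch decides the cut in a median 67% (scan-dated) to 80% (event-dated) of trials, so it is not a remote contingency. Loss is below 1 point in 72% (a) and 69% (b) of scenarios. The maxima sit in the corner of slowest accrual, shortest PFS and ORR 40%. Five unscanned participants occur in at most 0.5% of trials in any scenario.

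**Cross-check.** A simpler model used one exponential PFS for everyone, reading (a), events dated when they occur, and unscanned defined as before day 49. For accrual of 12 to 18 months and median PFS of 3 to 4 months, at least one participant is unscanned in 19% to 62% of event-triggered cuts, with a mean of 0.28 to 0.98 unscanned. At 1.43 points each that is about 0.4 to 1.4 points at p = 30%: the same order, at the upper end.

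**The case against.** **Materiality.** The effect is small against the sampling error. One responder in 21 is 4.8 points, so a median loss of 0.3 to 0.8 points is 0.06 to 0.17 of a responder. On the same grid, at least one eventual responder is missed in a median of about 5% of trials (scan-dated) or 13% to 14% (event-dated), so in the median scenario the primary ORR is unchanged in some 86% to 95% of trials. No hypothesis is tested, no numeric threshold is visible, and protocol 10.9.2 weighs safety, tolerability and other endpoints, DoR in particular. All of this stands and keeps the point minor.

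**Mitigation.** Unscanned participants can be identified through the best-response categories, the swimmer plot and the listings. Further cuts are possible and a final analysis is planned. The interim response evaluable set shows that the sponsor has recognised the issue. None of these changes the primary ORR: extra cuts are optional, the final analysis comes later, and the interim set is barred from the CSR.

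**Reading (a).** Footnote e and the planned 21 per cohort favour reading (b). That is fair, but waiting for the 21st dose does not give that participant a scan, and the losses under (b) are no smaller.

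**Late change.** The SAP's December 2023 amendment entry says an earlier visit derivation had confused interpretation of results, which suggests that outputs had been seen. Changing a cut rule in an open-label study at that stage needs a stated reason. This stands as a caution on how the fix is made.

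**Conclusion.** The point holds and is minor. As visibly written, the event branch can set the primary cut while dosed participants have not reached their first scheduled scan, and the ORR definition counts them as non-responders unless an unscheduled scan has already shown CR or PR. The mechanism follows directly from the text. Its size rests on assumed accrual and PFS: typically under 1 ORR point, and at most 3.6 points in the least favourable scenario examined. The scenario percentages are shares of an equally weighted grid, not probabilities.

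Three stronger readings are not supported:
- A reader might infer that the rule could make the drug look better. It cannot; the bias only lowers ORR.
- A reader might infer that an expansion decision would be misled. The documents show no ORR threshold that a loss of this size would cross, and ORR is not the only criterion.
- A reader might set the 21 participants of SAP 4.2.1 against protocol 10.4.1 ("after all response-evaluable participants in the cohort have had the opportunity to be followed for at least 6 months since their first dose") and see a second defect. That difference matters only for enrolment beyond 21, and text near those passages is redacted, so no conclusion can be drawn.

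**What to change.** In SAP 4.2.1, let the 75% branch (16 of the 21) trigger the cut only once the 21 response-evaluable participants are dosed and each meets one of these conditions:
- has had the opportunity for the Week 8 scan (day 63);
- has progressed or died;
- has started other anticancer therapy;
- has withdrawn from the study or been lost to follow-up.

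Stopping study treatment alone should not satisfy the condition, because those participants are still scanned and their responses still count. Starting other anticancer therapy should, because SAP 5.2.1.1 does not count a response first seen afterwards. Early progressors and early deaths stay in the denominator.

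Record the change and its reason in SAP Section 3, which already lists departures from the protocol. Make it before the cut it governs, since it can only raise the observed ORR or leave it unchanged. The protocol wording can follow at the next amendment, which needs ethics and regulatory approval.

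The cost is one clause and some time, with no added visits or scans. When the 16th event comes early, the cut moves to at most 63/7 = 9 weeks after the 21st first dose. Simulated mean delay is 0 to 1.4 months (median scenario 0.1 to 0.3) against a cut that already waits for 21 dosed. Against reading (a) it is 0 to 3.1 months (median 0.1 to 0.4), because dosing of the 21 must then finish first. The simulation has no treatment discontinuations, so it does not show how often that exclusion would matter.

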4.2.2 Analysis Populations

For purposes of analysis, the study populations are defined as provided in [Table 2](#).

All participants who received any amount of IP will be included in the safety population.

The following populations are defined:

Table 2 Populations for Analyses

Population/Analysis set	Description	Endpoint/Output
Enrolled	All participants who sign the ICF.	Disposition
Safety	All participants who receive any amount of any IP.	Exposure Safety PK concentrations and parameters listings
Full analysis set/ITT	All participants who receive any amount of any IP.	Baseline and demography PFS OS
Response evaluable	All dosed participants who have measurable disease at baseline.	ORR CR DoR
Interim response evaluable	All dosed participants with measurable disease at baseline that have had their first post-baseline disease assessment performed or have discontinued study treatment before the first post-baseline disease assessment. This analysis set will not be used for presentation in the CSR and is only defined for conferences and publications.	ORR at interim DoR at interim
PK	All participants who receive any amount of IP with at least one reportable concentration.*	PK concentrations PK parameters

Abbreviations: ICF, informed consent form; IP, investigational product; ITT, intention-to-treat; PK, pharmacokinetics; PFS, progression free survival; OS, overall survival; DoR, duration of response; ORR, objective response rate; CR, complete response.

* Individual PK concentration and parameter data values that are excluded from the descriptive summary tables and/or figures eg, due to important protocol deviations that might effect PK – are included in the listings and are flagged with an appropriate footnote.

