Statistical Methods: In Module 1, the data cut-off (DCO) for the primary analysis for each cohort will occur after all response-evaluable participants in the cohort have had the opportunity to be followed for at least 6 months since their first dose or have progressed or have initiated other anticancer therapy, or when 75% of participants have progressed or died, whichever occurs first. Additional data cuts may also be performed, if required. At the end of each module a final analysis will be conducted to incorporate all data (up to and beyond the primary analysis) from all participants in the module. For all modules, the primary efficacy endpoint is ORR. For Module 1, ORR is measured in terms of the Lugano criteria. Secondary efficacy endpoints for Module 1 include CR rate, DoR, PFS and OS. Safety and tolerability will be assessed in terms of AEs, laboratory data, vital signs and ECG data for all modules. AEs will be graded according to the NCI CTCAE Version 5.0. The number and percentage of participants with TEAEs in different categories (eg, causally related, CTCAE Grade ≥ 3 , etc.) will be summarised by cohort; events in each category will be further summarised by MedDRA system organ class and preferred term. SAEs will be summarised separately if a sufficient number occurs. Data will be presented by cohort. Descriptive statistics will be used for all variables. Continuous variables will be summarised by the number of observations, mean, standard deviation, median, minimum, and maximum. Categorical variables will be summarised by frequency counts and percentages for each category. Unless otherwise stated, percentages will be calculated based on the population total by cohort and by timepoint as appropriate.

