10.9.4.2 Efficacy Analyses

The efficacy endpoints of ORR, CR rate and DoR will be summarised on the response evaluable set. The efficacy endpoints of PFS and OS will be summarised on the full analysis set (ITT).

Additional subgroup analysis of efficacy may be performed as specified in the SAP.

The response criteria for malignant lymphoma ([Cheson et al 2014](#)) will be used, as assessed by investigators, to derive the endpoints (ORR, CR rate, DoR and PFS).

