5.2.2.2 Primary Analysis of Secondary Endpoint: CR Rate

CR rate will be calculated and binomial exact 2-sided CIs at 80% and 95% will be presented for participants in the response evaluable set.

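### The primary cut-off is timed on all response-evaluable participants in two protocol sections but on 21 in protocol 10.9.2 and SAP 4.2.1, and the ORR denominator takes in participants not yet scanned

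*SAP*

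**What the plan says.** **Cut-off.** Protocol 1.1 states that the primary DCO "will occur after all response-evaluable participants in the cohort have had the opportunity to be followed for at least 6 months", and protocol 10.4.1 uses the same wording. SAP 4.2.1 states that it "will occur after 21 response-evaluable participants in the cohort have had the opportunity to be followed for at least 6 months", and protocol 10.9.2 agrees. Every version adds the same alternatives: progression, other anticancer therapy, or 75% of participants progressed or died, whichever is first. None says 75% of whom. Footnote e to protocol Figure 5 mentions N = 21 and the 75% trigger in one sentence.

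**Planned number.** Protocol Table 19 and SAP Table 3 give 21 response-evaluable participants per cohort for the primary analysis, and the text beside them says approximately 21. Protocol 10.9.2 allows enrolment past the initial 21, to about 60 PTCL and 30 cHL participants. The conditions for doing so are redacted.

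**Analysis set.** SAP Table 2 defines the response evaluable set as "All dosed participants who have measurable disease at baseline"; protocol Table 22 has the same definition. ORR is "based upon the number of participants in the response evaluable analysis set" (SAP 5.2.1.2). For the secondary endpoint, "CR rate will be calculated and binomial exact 2-sided CIs at 80% and 95% will be presented for participants in the response evaluable set" (SAP 5.2.2.2). Protocol 10.9.4.2 groups the endpoints: "The efficacy endpoints of ORR, CR rate and DoR will be summarised on the response evaluable set". SAP Table 2 also defines an interim response evaluable set, which requires a first post-baseline assessment or earlier discontinuation of treatment, but adds: "This analysis set will not be used for presentation in the CSR and is only defined for conferences and publications".

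**First scan.** SAP Appendix A puts it at days 49–63.

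**Use.** Protocol 10.4.1: "If 1 or more cohorts show a favourable safety and efficacy profile by the primary analysis then further expansion cohorts may be added".

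**The concern.** Two current rules give different dates for the same analysis once a cohort passes 21. The study is open-label with investigator-assessed response, so the cut date should not depend on which section is consulted. The 75% trigger adds a second ambiguity of the same kind.

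The denominator is a separate matter. If the cut is timed on 21 while enrolment continues, everyone dosed by that day with measurable disease is in the ORR and CR-rate denominator. Someone dosed a month earlier cannot yet have a scheduled scan and counts as a non-responder. An early 75% cut can also leave unscanned participants among the 21. The one set that deals with unscanned participants is kept out of the CSR, so a publication and the CSR could report ORR on different denominators from the same cut.

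ORR is the primary endpoint and the expansion decision looks to this analysis.

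**Working it through.** **1. Stated totals.** 60 + 30 = 90 reproduces the stated maximum of about 90; 3 × 21 = 63. There is therefore room for 27 more, or 9 per cohort if the 60 PTCL places split equally (an assumption; 30 is stated for cHL). N = 21 itself cannot be re-derived: no hypothesis is stated and the precision tables are redacted.

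**2. The 75% trigger.** 0.75 × 21 = 15.75, so 16 events. 0.75 × 30 = 22.5, so 23 events.

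**3. Both cuts at 6 months.** Accrual is not given. Assume a steady r per month to 30 per cohort and 1 month = 30.44 days. Participant 21 + k (k = 1 to 9) is first dosed k/r months after the 21st.

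- Gap between the two cut dates = 9/r.
- Dosed by the 21-participant cut if k/r ≤ 6.
- Unscanned if (6 − k/r) × 30.44 < 56 days (or 63, the end of the window).
- Reported ORR for a true 30% = 30% × (dosed − unscanned)/dosed.

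| r per month | Gap, months | Dosed | Unscanned, day 56 / 63 | ORR reads, day 56 / 63 |
|---|---|---|---|---|
| 0.875 | 10.3 | 26 | 2 / 2 | 27.7% / 27.7% |
| 1 | 9.0 | 27 | 2 / 3 | 27.8% / 26.7% |
| 1.25 | 7.2 | 28 | 2 / 3 | 27.9% / 26.8% |
| 1.5 | 6.0 | 30 | 3 / 4 | 27.0% / 26.0% |
| 1.75 | 5.1 | 30 | 2 / 3 | 28.0% / 27.0% |
| 2 | 4.5 | 30 | 1 / 2 | 29.0% / 28.0% |
| 2.5 | 3.6 | 30 | 0 / 0 | 30.0% / 30.0% |
| 3 | 3.0 | 30 | 0 / 0 | 30.0% / 30.0% |

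**4. The 75% trigger may fire first.** Simulation with the same accrual rates, exponential PFS with median 2.5, 4 or 6 months (assumed), and 5,000 runs per setting. The 21-participant cut is the earlier of the 16th event in the first 21 and all 21 reaching 6 months or progressing. The all-participant cut is the same with 23 events of 30. Unscanned means dosed, event-free and under 56 (63) days from first dose.

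- Mean gap between cut dates: 2.2–8.1 months.
- All dosed at the 21-participant cut: mean 0.3–3.7 unscanned (0.4–4.1 with day 63; most seen 7). A true 30% reads 25.7–29.7% (25.3–29.6%). The low end needs 3 per month together with median PFS of 2.5 months.
- First 21 only: mean 0–1.4 unscanned (0–1.6; at most 5). A true 30% reads 27.9–30.0% (27.7–30.0%).

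**5. Scale against precision.** Exact (Clopper–Pearson) 80% limits are the Beta(x, n − x + 1) quantile at 0.10 and the Beta(x + 1, n − x) quantile at 0.90.

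- 8/27 = 29.6%: 18.1–43.6%.
- 8/30 = 26.7%: 16.2–39.7%, width 23.5 points.
- 6/21 = 28.6%: 15.8–44.8%, width 29.0 points.

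Three unscanned participants added to 8/27 move the estimate by about 3 points, well inside either interval.

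**The case against.** The rule for going past 21 is redacted, including footnotes to the tables and schema that give the 21. That text may say how later participants are handled, so the likelihood of the problem cannot be judged. This stands as a limit on the practical effect. It does not remove the conflict, because both DCO wordings, SAP Table 2 and SAP 5.2.1.2 are legible and current.

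The two wordings might also be read together: the sentence in protocol 10.4.1 introduces a table planning 21 per cohort, and the more detailed statistical sections say 21. That shows the likely intent and supports the choice of wording in the fix. It does not make the other two sections agree once a cohort reaches 22.

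Approximately 21 is not a hard cap, and an analysis-set table need not repeat a sample size. That is fair. The gap is the missing follow-up condition more than the missing number.

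A reader might infer that a hard cap at 21 is therefore required. The documents do not compel it. At 2.5–3 per month in the 6-month case, a cap would drop 9 scanned participants and avoid no unscanned ones, and the interval would widen as in step 5.

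A reader might also infer that DoR is distorted. It is not: SAP 5.2.3 summarises DoR in responders only, by Kaplan–Meier, and later responders enter with censored durations.

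**Conclusion.** The inconsistency is real and the severity is minor. The DCO has two current wordings, the 75% trigger has no stated base, and the ORR and CR-rate denominator has no minimum follow-up. The cut dates can differ only if a cohort enrols past 21. The denominator effect needs either that or an early 75% cut.

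Under the assumed accrual, 30 per cohort and exponential PFS, the cut dates differ by about 2–10 months and a true 30% ORR reads about 26–30% on average. The bias is downward and small against the interval. No hypothesis is tested and no decision threshold is visible. Success also weighs safety and DoR. The best-overall-response table and swimmer plot would show unscanned participants, and the final analysis takes everyone.

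A reader might fear a larger loss, such as 7/21 = 33.3% becoming 7/30 = 23.3%. That requires all nine later participants to have no response. The calculations do not support it as a typical result: in the 6-month case at most 3 or 4 of the nine are unscanned, and those already scanned can respond.

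**What to change.** **(a) One cut-off rule.** In protocol 1.1, 10.4.1 and 10.9.2 and SAP 4.2.1, time the DCO on the first 21 response-evaluable participants by first-dose date. State that the 75% trigger is counted on those 21 (16 events).

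**(b) One follow-up-complete analysis in the CSR.** In SAP 4.2.2, 5.2.1.2 and 5.2.2.2, add ORR and CR rate in response-evaluable participants first dosed at least 63 days before the DCO. First-dose date alone sets membership. Everyone in that group counts, including those who progressed, died or discontinued before a scan, and nobody dosed later is added because of an early event. The existing interim set would not serve, because it admits recent participants who discontinue early while leaving out recent participants still on treatment and awaiting a scan. Show the first-21 and all-dosed results beside it, and state before database lock which is primary.

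Capping the primary set at 21 is optional, given its cost in precision.

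**Cost.** Wording changes and one or two extra tables; no extra participants, procedures or visits. An early 75% cut can still leave a few unscanned participants among the first 21; the analysis in (b) shows their effect.
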